### **10.1.4 Dose Selection**

Dose selection for the further development will be based on the following efficacy and safety considerations; more than 1 dose may meet these criteria. An effective dose, or dose regimen, will be one that achieves clinically-meaningful reduction in plasma Lp(a) levels. Safety will be evaluated on the basis of incidence of expected and unexpected treatment-related SAEs and other specific safety considerations including the incidence of platelet reductions, and renal or hepatic injury.

### **10.2 Sample Size Considerations**

Based upon prior clinical trial experience with ISIS 681257, it is estimated that the standard deviation of the percent change in Lp(a) is approximately 20%. With 23 patients in each ISIS 681257 treatment group and 23 in placebo group there would be approximately 90% power to detect a 20% difference in percent change in Lp(a) levels between the ISIS 681257 treatment groups and placebo group at an alpha level of 0.05, assuming 30% reduction in the ISIS 681257 patients and 10% reduction in the placebo patients.

Based upon prior clinical trial experience with Ionis ASOs, assuming the incidence rate of platelet count below lower limit of normal (LLN) in placebo treated patients is 1.9%, in the ISIS 681257 treated patients is 3.8%, twice the incidence rate observed in placebo, with 45 patients in each ISIS 681257 treatment group, there would be approximately 80% power to detect at least 1 event.

Therefore, approximately 270 patients (54 patients per cohort, including 45 patients per cohort treated with ISIS 681257) will be randomized to ensure that both the safety and efficacy of ISIS 681257 will be adequately characterized in the study.

### **10.3 Analysis Populations**

Full Analysis Set (FAS): All patients who are randomized, received at least 1 dose of Study Drug (ISIS 681257 or placebo), and have a Baseline Lp(a) assessment. The FAS represents the practically-feasible intent-to-treat (ITT) population as delineated in ICH Guideline E9. This population will be used for the primary analysis of efficacy.

Per Protocol Set (PPS): Subset of the FAS who received within 6 months at least 5 monthly doses of Study Drug for patients randomized in Cohorts A, B, and C or at least 20 weekly doses for patients randomized in Cohorts D and E, and who have no major protocol violations that could compromise the interpretation of efficacy. Major violations will be determined prior to unblinding for statistical analysis. This population will be used for supportive inferences concerning efficacy.

Safety Set: All patients who are randomized and receive at least 1 dose of Study Drug. This population will be used for all safety analyses.

PK Population: All patients who are randomized and received at least 1 dose of Study Drug, and have sufficient data for the analysis of PK parameters. This population will be used for analysis of PK data.

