Following SC administration, ISIS 681257 was absorbed rapidly into the systemic circulation, with median time to maximum plasma concentrations ( $T_{max}$ ) ranging from 1 to 4 hours. Similar  $T_{max}$  values were observed at all dose levels. Maximum observed plasma concentrations ( $C_{max}$ ) and  $AUC_{0-24hr}$  were dose-dependent over the studied SC dose range. The mean peak ( $C_{max}$ ) and total exposure ( $AUC_{0-24hr}$ ) increased proportionally with dose at dose levels ranging from 10 to 40 mg, and greater than dose proportionally at dose levels ranging from 40 to 120 mg.

After reaching  $C_{max}$ , mean plasma concentrations of ISIS 681257 declined in a biphasic fashion over time, with an initial, relatively fast distribution phase that dominated the plasma clearance followed by a slower elimination phase. Characterization of the terminal elimination phase yielded an apparent terminal elimination half-life of approximately 3 to 4 weeks over a dose range of 10 to 120 mg (either single- or multiple-dose), and appeared to be independent of dose. This result is consistent with the slow elimination of ISIS 681257 observed from monkey tissues, and the comparatively long elimination half-lives observed for this chemical class.

Plasma trough concentrations (168 hours or 7 days from previous dose) monitored during the treatment period in the multiple-dose cohorts increased with increasing dose, consistent with expectations (based on preclinical assessments and experience with other compounds of this chemical class) that trough plasma concentrations reflect exposure in tissues. Plasma trough concentrations did not increase greatly after the loading period (Day 15), suggesting that accumulation in major tissues of distribution had approached steady-state after the loading period.

Overall, the human PK of ISIS 681257 are consistent with the expected PK for compounds within this chemical class.

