### 3. EXPERIMENTAL PLAN

#### 3.1 Study Design

This is a Phase 2, multicenter, randomized, double-blind, placebo-controlled, dose-ranging study. Approximately 270 patients will be randomized in a 5:1 ratio (225 ISIS 681257 and 45 placebo) to receive ISIS 681257 or placebo. Study Drug (ISIS 681257 or placebo) will be administered SC every week, every 2 weeks (biweekly), or every 4 weeks, depending on cohort assignment, for up to 52 weekly doses, up to 26 every 2-week doses, or up to 13 every-4-week doses.

The primary analysis time point is at Week 25 for patients who received every 4-week dosing (Cohorts A-C) and at Week 27 for patients who received 2-week or weekly dosing (Cohorts D and E). For patients continuing treatment beyond the primary analysis time point additional supportive efficacy analysis (to evaluate whether the treatment effect is maintained) and safety analysis (for the purpose of dose(s) selection) will be repeated at the completion of Study Drug treatment.

The treatment portion of the study will be complete when the last enrolled patient reaches 6 months of exposure. All patients will then enter a 16-week post-treatment follow-up period.

Patients  $\geq 18$  and  $\leq 80$  years old with elevated plasma Lp(a) levels ( $\geq 60$  mg/dL ) and a clinical diagnosis of CVD are eligible for enrollment upon meeting the study specific eligibility criteria. Patients will be on standard-of-care preventative therapy for other than elevated Lp(a) CVD risk factors as per current guidelines.

Clinical diagnosis of CVD is defined as documented coronary artery disease (CAD), stroke, or peripheral artery disease (PAD). A diagnosis of CAD has to be documented by any of the following:

- Angiographic evidence of  $\geq 50\%$  stenosis of 1 or more major epicardial coronary arteries
- History of myocardial infarction documented by positive enzymes, and either symptoms of myocardial ischemia, or ECG changes ([Thygesen et al. 2012](#))
- History of coronary revascularization
- Evidence of cardiac ischemia on exercise testing, or imaging study

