**Table 3 Actions in Patients with Low Platelet Count**

Platelet Count on Rx	Drug Dose	Monitoring
Normal range, > 140K/mm 	No action	Monitor every 2 weeks
100K-140K/mm 	No action	Closer observation Monitor every week*
75K-100K/mm 	Permanently reduce as follows: For Cohort A: reduce to 10 mg every 4 weeks For Cohort B: reduce to 20 mg every 4 weeks For Cohort C: reduce to 30 mg every 4 weeks For Cohort D: reduce to 10 mg every 2 weeks For Cohort E: reduce to 10 mg every week	Closer observation Monitor every week*
50K-75K/mm 	Pause dosing When platelet count returns to > 100K/mm  restart dosing as follows only if approved by Sponsor Medical Monitor: For Cohort A: reduce to 10 mg every 4 weeks For Cohort B: reduce to 20 mg every 4 weeks For Cohort C: reduce to 30 mg every 4 weeks For Cohort D: reduce to 10 mg every 2 week For Cohort E: reduce to 10 mg every week or Permanently discontinue Study Drug if it occurs while on already reduced dose	Closer observation Monitor every 2-3 days until 2 successive values show improvement Consider discontinuation of antiplatelet agents/non-steroidal anti-inflammatory drug (NSAIDS)/ anticoagulant medication
25K-50K/mm 	Permanently discontinue Study Drug	Closer observation: Monitor daily until 2 successive values show improvement then monitor every 2-3 days until platelet count stable Discontinue antiplatelet agents/NSAIDS/anticoagulant medication while platelet count < 50K/mm  if possible
< 25K/mm 	Permanently discontinue Study Drug	Closer observation: Monitor daily until 2 successive values show improvement then monitor every 2-3 days until platelet count stable Steroids recommended** Consider need for hospitalization and referral to hematologist Discontinue antiplatelet agents/NSAIDS/anticoagulant medication while platelet count < 50K/mm  if possible

\* Once a patient commences weekly monitoring this frequency of monitoring should continue irrespective of whether the platelet count rises into the normal range.

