**Appendix A Schedule of Procedures – Every 4-Week Dosing *Continued***

	Screen	Treatment Period																			Follow-up Period			
Study Week	-4 to -1	1	1	5	9	13	17	21	25		26	27	29	33	37	41	45	49	53/ET	4*	10*	16*		
Study Day	-28 to -1	1	2 a	29	57	85	113	141	169	170 a	171 a	176 a	183 a	197	225	253	281	309	337	365	*Post Last Dose			
Visit Window +/- Days	0	-3 b	0	2	2	2	3	3	3	0	0	3	3	3	3	3	3	3	3	3	3	3	3	
FSH (women only, if applicable) i, m	X																							
Serum Pregnancy Test m	X	X		X	X	X	X	X	X					X	X	X	X	X	X	X	X	X	X	
Archived Serum & Plasma Samples j, n		X		X		X		X					X		X		X		X		X	X	X	
PD Panel l	X	X		X	X	X	X	X	X				X	X		X		X		X	X	X	X	
Lipid Panel l	X	X		X	X	X	X	X	X			X	X	X		X		X		X	X	X	X	
Lp(a) Characterization		X																						
Study Drug: SC Injection		EVERY 4-WEEK SUBCUTANEOUS ADMINISTRATION OF STUDY DRUG (Week 1 through Week 49/Day 337) o																						
Adverse Events	X	X	X	X	X	X	X	X	X	X	X			X	X	X	X	X	X	X	X	X	X	
Concomitant Medication	X	X	X	X	X	X	X	X	X	X	X			X	X	X	X	X	X	X	X	X	X	

All procedures and study samples are to be done pre-dose at respective visits, unless specified

- a Visit only required for patients in PK subgroup.
- b Day 1/Baseline assessments can be performed up to 3 days (-3 days) prior to the actual Day 1 visit, which is the day of first Study Drug dose.
- c Patient charts will be reviewed in order to collect disease associated medical history data such as CVD history.
- d Height only required at Screening.
- e All tests listed in Appendix B under Extended Urinalysis should be performed, including routine urinalysis, urine microscopy, UACR and UPCR.
- f Assessments and procedures to be conducted by either a home healthcare service or the Study Center. Patient Study Center visits must be no more than 4 weeks apart during the treatment period.
- g Urine samples for renal biomarkers will be collected. Sample analysis will be conducted in accordance with Safety Monitoring for Renal Function (Section 8.5.2).
- h During follow-up period, hematology sampling for platelet values and urine renal biomarker samples are taken every 14 days for 6 weeks after last dose of Study Drug, then every 6 weeks.

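### The Per Protocol dose count for Cohorts A–C can be met with a dose given after the Week 25 sample

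*Protocol*

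**What the plan says.** Section 10.3 of the Protocol admits a Cohort A–C patient to the PPS on two conditions. The patient must have "received within 6 months at least 5 monthly doses of Study Drug for patients randomized in Cohorts A, B, and C", and must be among those "who have no major protocol violations that could compromise the interpretation of efficacy". The length of the window is not given in days. On the role of the set, the section says: "This population will be used for supportive inferences concerning efficacy". Section 10.6.3.1 uses it for two sensitivity analyses of the primary endpoint (the repeated ANCOVA and the Wilcoxon/Hodges-Lehmann analysis). Section 10.6.3.2 uses it as the supporting set for the secondary endpoints.

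Section 3.1 places the primary analysis at Week 25 for Cohorts A–C and at Week 27 for Cohorts D and E. In Appendix A these visits are Day 169 and Day 183. The notes to the every-4-week schedule fix the order of events on a visit day: "All procedures and study samples are to be done pre-dose at respective visits, unless specified". Section 2.3.4 reports an "apparent terminal elimination half-life of approximately 3 to 4 weeks".

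**The concern.** A per-protocol set should be defined by exposure that could have shaped the outcome being analysed. Here the Week 25 sample comes before the Day 169 injection, yet that injection may supply the fifth qualifying dose. A patient dosed on Days 1, 29, 57 and 85, not dosed on Days 113 and 141, and dosed again on Day 169 has five doses. At the sample, that patient has gone 84 days without drug.

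The protocol's own rules can produce such a gap. Table 3 pauses dosing at platelet counts of 50K to 75K, Section 8.5.2 interrupts dosing on a confirmed renal alert, and Section 6.2.1 holds dosing when platelet or renal results are missing. At stake is how well the PPS analyses show the effect of the regimen as assigned.

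**Working it through.** **Schedule.** Every-4-week doses fall on Day 1 + 28k, with the last on Day 337 (Appendix A). That gives (337 − 1)/28 + 1 = 13 doses, which matches the maximum of 13 in Section 8.1. Up to the endpoint visit the dosing days are 1, 29, 57, 85, 113, 141 and 169. The first six precede the sample and the seventh follows it.

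**Which doses count.** The protocol converts months to weeks in two ways.
- Section 3.4.2 gives the maximum treatment period as 52 weeks and as 12 months. Six months is then 26 weeks, or 182 days. Day 169 is inside, and seven doses count.
- Section 3.4 equates 18 months with 72 weeks, that is 72/18 = 4 weeks per month. Six months is then 24 weeks, Days 1 to 168. Day 169 is just outside, unless the visit falls early within its 3-day window.

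On the first reading, 5 − 1 = 4 of the six pre-sample doses are enough. The cumulative dose before the sample is then 4/6 = 67% of plan.

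**Residual drug at the sample.** Let h be the half-life in days and r = 2^(−28/h). The Day 141 dose contributes r, Day 113 contributes r², and so on to r⁶ for Day 1. The planned residual is S = r + r² + … + r⁶. With Days 113 and 141 missed, the share left is (r³ + r⁴ + r⁵ + r⁶)/S.
- h = 21: r = 0.3969 and S = 0.6554, so the share is 0.1011/0.6554 = 15.4%.
- h = 24.5: 19.8%.
- h = 28: r = 0.5 and S = 63/64, so the share is (15/64)/(63/64) = 15/63 = 23.8%.

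**Other patterns.** There are 15 ways to miss two of the six doses. The last two rows show what remains if only one pre-sample dose may be missed.

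| Pre-sample doses missed | h = 21 days | h = 28 days |
|---|---|---|
| Days 113 and 141 (worst of 15) | 15% | 24% |
| Day 141 and any one other (5 patterns, including the worst) | 15–39% | 24–48% |
| Any two, Day 141 given (10 patterns) | 66–98% | 62–95% |
| Day 141 only | 39% | 49% |
| Day 113 only | 76% | 75% |

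Requiring 5 of the 6 pre-sample doses therefore raises the worst case from 15–24% to 39–49% (Day 141 missed, share 1 − r/S). Also requiring the Day 141 dose raises it to about 75% (Day 113 missed, share 1 − r²/S).

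**The case against.** **The window may exclude Day 169.** On a 24-week reading the rule is already 5 of the 6 pre-sample doses. This stands in part: the text permits that reading but does not settle it, and the protocol's 52-week year points the other way.

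**The violation clause may catch these patients.** Missing the last two doses before the primary sample could be ruled a major violation, and the criteria may be set in the SAP, which is not shown. That may remove patients who simply missed visits. It would not reliably remove patients whose doses were withheld as the protocol directs, since such a hold is not in itself a violation.

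**The example is extreme.** This stands. The 15–24% is the lowest of 15 patterns. How often it would occur is unknown, and Section 8.1 allows a missed injection to be rescheduled.

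**Stronger readings a reader might infer, which the documents do not support:**
- *That such patients are in effect untreated.* Section 2.4 predicts reductions of about 60% at the equivalent of 5 mg weekly and 85% at 20 mg, so a fourfold lower exposure still gives a large effect. As an illustration, assume reduction = dose/(dose + 3.3), which passes close to both predictions. Cohort C at 15–24% of 15 mg (2.3 to 3.6 mg weekly) would then keep a reduction of about 41–52%. Cohort A would keep less. The share of drug remaining is not the share of Lp(a) effect remaining.
- *That patients on reduced doses should also leave the PPS.* Table 3 prescribes these reductions, for example "For Cohort C: reduce to 30 mg every 4 weeks". Patients who follow them are treated as the protocol directs. Removing them would condition on a post-randomization safety event that may be drug-related.
- *That Cohorts A–C face a laxer bar than Cohort E.* If the endpoint-visit dose counts in both, the minimum is 4/6 (67%) against 19/26 (73%). If it counts in neither, it is 5/6 (83%) against 20/26 (77%). The order reverses, so no such claim can be made.

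**Conclusion.** The point holds in a limited form. On a calendar reading of the six-month window, a dose given after the endpoint sample can qualify a Cohort A–C patient for the PPS, and four of the six doses that can affect the endpoint are then enough. In the worst pattern, 15–24% of the planned residual drug is left at the sample.

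That range assumes first-order superposition and takes the Phase 1 terminal plasma half-life of 3 to 4 weeks as applying here. It describes drug remaining at the sample, not cumulative dose (67%) and not Lp(a) response. No dilution of the PPS estimate can be calculated, because the frequency of such patterns is not known. The primary analysis, in the Full Analysis Set, is untouched. This is a poorly fixed rule for a supportive set, and it is worth correcting because the correction is cheap.

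**What to change.** Rewrite the PPS dose condition in Section 10.3, and carry it into the SAP before unblinding, so that it counts only doses scheduled before the primary sample:
- Cohorts A–C: at least 5 of the 6 doses due before Day 169.
- Cohorts D and E: proportionate counts of the doses due before Day 183. These number 13 and 26, and five sixths of them is 10.8 and 21.7, so 11 and 22 if rounded up.
- Preferably, also require that the last scheduled dose before the sample was given.

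Patients on Table 3 reduced doses need not be excluded. The same sentence also sets Cohort D's threshold in weekly doses although that cohort is dosed every 2 weeks. That is a separate matter, but the rewrite can settle it too.

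The cost is a sentence or two of text and a slightly smaller PPS. No change to conduct, sample size or the primary analysis is needed.

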## **8. TREATMENT OF PATIENTS**

### **8.1 Study Drug Administration**

ISIS 681257 will be administered to patients by Study Center staff as follows:

- Cohort A: a single SC dose of 20 mg once every 4 weeks for up to 52 weeks and a maximum of 13 doses
- Cohort B: a single SC dose of 40 mg once every 4 weeks for up to 52 weeks and a maximum of 13 doses
- Cohort C: a single SC dose of 60 mg once every 4 weeks for up to 52 weeks and a maximum of 13 doses
- Cohort D: a single SC dose of 20 mg every 2 weeks for up to 52 weeks and a maximum of 26 doses
- Cohort E: a single SC dose of 20 mg every week (weekly) for up to 52 weeks and a maximum of 52 doses

Self-administration will be allowed after appropriate training of patient and/or caregiver.

Patients in Cohorts A, B, and C should receive 1 dose every 4 weeks, patients in Cohort D should receive 1 dose every 2 weeks and Cohort E should receive 1 dose per week with weeks always defined relative to Study Day 1. For example if a patient receives the first dose on a Monday, subsequent doses should be given on Mondays according to the respective dosing schedule, if possible. If a patient misses an injection, or if dosing on the usual day is not possible, the patient can reschedule the injection provided that 2 doses are administered at least 2 days apart.

Every effort should be made to ensure the previous dose is given 7 days prior to a scheduled clinic visit.

Please refer to the Study Drug Manual provided by the Sponsor or designee for more detailed instructions for Study Drug (ISIS 681257 or placebo) preparation and administration.

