**Table 2 Study Drug Dosing Information**

Cohort	Treatment	Volume to Administer/Dose	# Doses	Total ISIS 681257
A	20 mg ISIS 681257 or placebo (Every 4 weeks)	0.2 mL	≤ 13	≤ 260 mg
B	40 mg ISIS 681257 or placebo (Every 4 weeks)	0.4 mL	≤ 13	≤ 520 mg
C	60 mg ISIS 681257 or placebo (Every 4 weeks)	0.6 mL	≤ 13	≤ 780 mg
D	20 mg ISIS 681257 or placebo (Every 2 weeks)	0.2 mL	≤ 26	≤ 520 mg
E	20 mg ISIS 681257 or placebo (Every week)	0.2 mL	≤ 52	≤ 1040 mg

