### **10.6.3 Efficacy Analysis**

#### **10.6.3.1 Analysis of Primary Efficacy Endpoint**

The primary analysis of the primary endpoint will be the pairwise comparison of percent change from baseline to primary analysis time point in fasting Lp(a) between ISIS 681257 treatment groups and pooled placebo group in the FAS. The data will be analyzed using an analysis of covariance (ANCOVA) model with the Baseline Lp(a) as a covariate. Missing data may be handled by LOCF or multiple imputation methods ([Schafer 1997](#); [Schafer 1999](#)).

The primary efficacy analysis will take place after the last patient has completed the primary analysis time point and at least 50% of randomized patients have completed Week 52 visits, and the database has been locked,

The following sensitivity analyses will be conducted:

- The primary analysis will be repeated in the PPS
- The primary efficacy endpoint will be analyzed using a Wilcoxon Rank Sum test on both FAS and PPS, and the treatment effect will be estimated using Hodges-Lehmann estimator

Additional sensitivity analyses may be conducted as appropriate; the details of these analyses will be outlined in the SAP.

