#### **10.3 Analysis Populations**

Full Analysis Set (FAS): All patients who are randomized, received at least 1 dose of Study Drug (ISIS 681257 or placebo), and have a Baseline Lp(a) assessment. The FAS represents the practically-feasible intent-to-treat (ITT) population as delineated in ICH Guideline E9. This population will be used for the primary analysis of efficacy.

Per Protocol Set (PPS): Subset of the FAS who received within 6 months at least 5 every 4-week doses of Study Drug for patients randomized in Cohorts A, B, and C or at least 10 every 2-week doses for patients randomized in Cohort D or 20 weekly doses for patients randomized in Cohort E, and who have no major protocol violations that could compromise the interpretation of efficacy. Major violations will be determined prior to unblinding for statistical analysis. This population will be used for supportive inferences concerning efficacy.

Safety Set: All patients who are randomized and receive at least 1 dose of Study Drug. This population will be used for all safety analyses.

PK Population: All patients who are randomized and received at least 1 dose of Study Drug, and have sufficient data for the analysis of PK parameters. This population will be used for analysis of PK data.

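### In the Amendment 4 text, the Per Protocol Set rule asks every-2-week Cohort D for 20 weekly doses within 6 months, which no on-schedule patient can reach

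*Protocol*

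**What the plan says.** Section 10.3 (Analysis Populations) of the Amendment 4 text defines the PPS by a dose count inside a fixed window and by freedom from major protocol violations. For Cohorts A to C the rule reads "Subset of the FAS who received within 6 months at least 5 monthly doses of Study Drug". For the other two cohorts it is a single shared minimum: "at least 20 weekly doses for patients randomized in Cohorts D and E".

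Section 8.1 of the same text gives these two cohorts different schedules. One entry reads "Cohort D: a single SC dose of 20 mg every 2 weeks for up to 52 weeks and a maximum of 26 doses"; the other reads "Cohort E: a single SC dose of 20 mg every week (weekly) for up to 52 weeks and a maximum of 52 doses". The same section adds that "patients in Cohort D should receive 1 dose every 2 weeks". Table 2, Section 6.1.2 and the synopsis agree that Cohort D is an every-2-week cohort.

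The PPS has three uses. In Section 10.6.3.1, "The primary analysis will be repeated in the PPS", and the Wilcoxon rank sum test with the Hodges-Lehmann estimate is run on both the FAS and the PPS. In Section 10.6.3.2, the PPS is the supportive set for every secondary endpoint.

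The other full protocol text in the file, dated 9 December 2016, doses Cohort D in the same way but separates the two cohorts in its Section 10.3: "at least 10 every 2-week doses for patients randomized in Cohort D", with 20 weekly doses for Cohort E.

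**The concern.** The PPS sentence and the dosing section of one protocol version cannot both be followed. A patient who keeps exactly to the Cohort D schedule fails the dose count. A patient who somehow met it would have been dosed more often than assigned, and so would be exposed to exclusion under the other half of the definition, the absence of major violations.

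At stake is the per-protocol evidence for one of five regimens. Cohort D matters to the design: Section 2.4 sets 20 mg every 2 weeks beside 40 mg every 4 weeks to see whether similar monthly exposure at different frequencies gives similar safety and similar Lp(a) reduction. There is also a spill-over. Placebo is pooled across cohorts, so excluding the Cohort D placebo patients shrinks the PPS control group for the other four regimens.

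**Working it through.** **Inputs (Amendment 4 text).** Dosing intervals and 52-week maxima: Section 8.1 and Table 2. PPS minimum and 6-month window: Section 10.3. Cohort size of 54, of whom 45 are active: Section 10.2, which leaves 54 − 45 = 9 on placebo. Primary time point for Cohorts D and E: Week 27, shown as Day 183 in Appendix A. I take 6 months as 26 weeks (182 days) and also show the count through Day 183.

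**Formula.** Scheduled doses fall on days 1, 1 + k, 1 + 2k, and so on, with k = 28 for A to C, 14 for D and 7 for E. The m-th dose falls on day 1 + (m − 1)k.

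**Reproducing the protocol's own figures.** Counting dose days through Day 364 gives 13 (A to C), 26 (D) and 52 (E). These match the stated maxima exactly.

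**Applying the count to the PPS window.**

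| Cohort | Doses through Day 182 | Doses through Day 183 | PPS minimum | Day the minimum is reached |
|---|---|---|---|---|
| A to C | 7 | 7 | 5 | 1 + 4×28 = 113 |
| D | 13 | 14 | 20 | 1 + 19×14 = 267 |
| E | 26 | 27 | 20 | 1 + 19×7 = 134 |

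Cohort D falls short by 20 − 14 = 6 or 20 − 13 = 7 doses. The 3-day visit window does not help: through Day 186 the count is still 14. The fifteenth dose falls on Day 1 + 14×14 = 197.

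**Could rescheduling rescue it?** Twenty doses by Day 183 would need one every 182/19 = 9.6 days. Section 8.1 lets a missed injection be moved, with at least 2 days between doses, but it gives no extra doses.

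**Effect on the set.** Cohort D contributes 0 of 54 patients (0 of 45 active, 0 of 9 placebo). The PPS can hold at most 5×54 − 54 = 216 of 270 patients. Pooled placebo can hold at most 45 − 9 = 36, a loss of 9/45 = 20%.

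**Effect on the other cohorts' PPS comparisons.** With 45 active patients and equal standard deviations, the standard error grows by the factor √[(1/45 + 1/36)/(1/45 + 1/45)] = √(0.0500/0.0444) = √1.125 = 1.06, about 6%. Under the Section 10.2 planning values (difference 20, standard deviation 20, two-sided 5%), t-test power moves from 99.7% at 45 against 45 to 99.3% at 45 against 36. That loss is small. The material loss is in Cohort D.

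**Checking a workable minimum.** Ten every-2-week doses are reached on Day 1 + 9×14 = 127. Ten of 13 is 77%, the same fraction as 20 of 26 (77%) for Cohort E and near 5 of 7 (71%) for A to C.

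**The case against.** The arithmetic is not in dispute. The case on the other side concerns weight and certainty, and much of it stands.

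First, the PPS is only supportive. The primary analysis is on the FAS, secondary endpoints use the FAS first, and neither the sample size nor the dose-selection text rests on the PPS. A reader might infer that Cohort D is left with no supportive analysis at all. The protocol does not support that: the Wilcoxon/Hodges-Lehmann analysis is also run on the FAS, and Sections 3.1 and 10.1 plan further supportive efficacy analyses at the end of treatment with no PPS restriction.

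Second, a reader might infer that a Cohort D patient could never receive 20 doses. That too goes beyond the text. Up to 26 are allowed over 52 weeks; the 6-month window is what makes the rule impossible.

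Third, this looks like a drafting slip that a later document could catch. Section 10 promises a detailed SAP, and Section 10.3 settles major violations before unblinding. Reading the rule as 20 weeks of dosing would give 20/2 = 10 doses for Cohort D and would work. An empty Cohort D PPS in the final analysis is therefore a consequence of the rule as written, not a forecast. But the sentence counts doses, and Section 10 says the SAP will incorporate these sections, so a SAP would either inherit the error or depart from the protocol.

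Fourth, the origin is inferred. The Amendment 4 log says a 10 mg weekly cohort became an every-2-week cohort, which fits wording left unrevised, but it does not name Cohort D. The 9 December 2016 text calls itself Amendment 3, whereas the Amendment 4 log dates Amendment 3 to 30 December 2016, so the sequence of drafts is unclear.

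Fifth, the file is part 2 of 2. The appendix pages ahead of Amendment 4 come from another version, because their Appendix E orders its tests differently. That version may be later than Amendment 4, and its Section 10.3 is not shown.

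**Conclusion.** The point holds for the Amendment 4 text. Its PPS rule contradicts its own dosing section and, applied literally, admits none of the 54 Cohort D patients. Lost for Cohort D are the PPS repeat of the primary ANCOVA, the PPS Wilcoxon/Hodges-Lehmann analysis and the PPS secondary analyses. PPS comparisons for Cohorts A, B, C and E can still be run, with up to 9 of 45 pooled placebo patients missing. The FAS primary and secondary analyses, the FAS Wilcoxon analysis and the end-of-treatment supportive analyses are untouched.

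This should be fixed, but it does not endanger the trial's main conclusion. The counts assume dosing on schedule, 6 months taken as about 26 weeks, and planned cohort sizes; any window ending before Day 197 gives at most 14 doses. The finding rests on the conflict inside Amendment 4, not on the difference from the 9 December 2016 text, which serves only to show that a workable wording exists. Whether a later version already corrects the rule cannot be checked from this file.

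**What to change.** Before unblinding, revise the PPS sentence in Section 10.3, and carry it into the SAP, so that Cohort D has its own minimum counted in every-2-week doses and the 20-weekly-dose minimum applies to Cohort E alone. At least 10 every-2-week doses within 6 months is a natural choice: it matches Cohort E proportionally and is the threshold in the 9 December 2016 text. If a version later than Amendment 4 exists, first check whether it already says this.

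The cost is one sentence. The change concerns membership of an analysis set only; dosing, visits and data collection stay as they are. Making it before unblinding avoids the appearance of choosing the population after seeing the results.
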